- An additional data presentation will consist of results from both Treatment and Control
 in similar studies appearing in the literature. There will be no formal statistical
 comparison of results from this study and historical studies.

4 Study Design

The present study will be a prospective, one arm observational study. Patients will begin taking the capsules at the onset of headache symptoms. Onset is defined as the time the participant takes the test product for relief of symptoms. When the participant decides to take the test product, they will report symptoms in the headache diary immediately before to taking the product and rate their symptoms on a 10-point Mankoski scale. After consuming the product, the participant will complete a Mankoski scale at 15 minutes, 30 minutes and 1 hour after taking the product. If needed the participant will be allowed to take alternative medication (alternative treatment) after an hour after taking the product. If alternative medication is taken, the participant will record this in their headache diary.

Study enrollment and management will be de-centralized, where participants do not visit an investigator or a clinic for clinical assessment. The participants will participate in the study at home.

All data collected from during this study will be reported by the patient via eCRFs, eDiary, and other electronic data entries. If a visit is required, it will be conducted via remote contact by telephone.

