4.2 Required Behavior

During the 1 hour after taking the test product, no medication or supplementation (including all CBD products) other than the test product should be taken. Once the 1-hour report has been submitted the patient may take other medications.

Patients are asked to limit the consumption of alcohol beverages to less than or equal to two drinks per day and to abstain from the use of cannabis for the duration of the study.

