4.3 Participation Period

Participants are expected to participate in the study for 60 days after study start. The product may be used after each onset of tension headache, but not more often than three times per day. Patients will be discontinued from the study 60 days after study start or after three recorded headache episodes. Study start is defined as the day the participant received the test product and completed the receipt of test product form.

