- After completing the surveys, the participant will take test product. The participant will take 2 capsules with 6-8 oz. of water per headache episode. With a max of 6 pills per day. (If participant takes 6 pills in 1 day this will be defined as 3 headache episodes and the patient will be exited from the study).
- After taking the test product, the participant will complete a Mankoski pain scale at 15 minutes, 30 minutes, and 1 hour after taking the test product.
- Once the participant's symptoms resolve, the participant will complete the headache diary.
- If the participant takes any other medication outside of the test product, the participant will record this on the headache diary.
- After taking the test product, the participant will be instructed to fill out an Adverse Event form for any side-effects experienced.
- After the first headache episode, the participant will be asked to complete the same process for another 2 headache episodes; however, these are not required.
- If the participant completes the required assessments for a total of 3 headache episodes, they will be prompted, by email, to exit the study.

- If the participant only completes the required assessments for the required 1 headache episode, the participant will be prompted, by email, to complete the study exit form and will be exited from the study on day 60 (60 days from the day of receipt of the test product).
- The sponsor nor Hawthorne Effect Inc. will not make any attempt to collect any unused product.
- Upon receipt of study exit survey and review of completed study forms, participant will receive an Amazon gift card of \$25 via email.

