6.2 Study Schedule of activities

Assessments	Screening	Consent	Before Receipt of Test Product	Product Received	Event 1	15 Minutes After Event Start	30 Minutes After Event Start	60 Minutes After Event Start
Study Window								
Screening Survey	Х							
Consent		X						
Baseline Survey			Х					
Demographics			Х					
Medications & Supplements			Х					
Acknowledgement of receipt of test product				X				
Headache Diary					X			X
10-point Mankoski Scale					Х	Х	Х	Х
Test Product Consumed					Х			
AE Assessment					X	X	X	X
Study Exit Survey								

Assessments	Event 2	15 Minutes After Event Start	30 Minutes After Event Start	60 Minutes After Event Start	Event 3	15 Minutes After Event Start	30 Minutes After Event Start	60 Minutes After Event Start	Study Exit
Study Window									
Screening Survey									
Consent									
Baseline Survey									
Demographics									
Medications & Supplements									
Acknowledgement of receipt of test product									
Headache Diary	Х			X	Х			X	
10-point Mankoski Scale	X	X	Х	X	X	X	X	X	
Test Product Consumed	Х				X				
AE Assessment	Х	X	Х	X	X	X	Х	X	Х
Study Exit Survey									X

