6.6 Test Product Packaging/Handling/Storage/Accountability

- The three-episode supply of test product will be packaged and labeled with ingredients and a study ID number.
- Participants will receive guidance on how to report receipt, store, and use the test product.
- Hawthorne Effect Inc. will support storage and shipment of test product, documentation of test product assignment, and completion of test product accountability.

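### Onset is defined as dosing and six pills in a day as three headaches, so repeat doses for one unresolved headache could be counted as new headaches in secondary analyses

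*Combined protocol and SAP*

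**What the plan says.** Sections 4 and 6.1 both state: "Onset is defined as the time the participant takes the test product for relief of symptoms". Section 4.3 builds on that word: "The product may be used after each onset of tension headache, but not more often than three times per day". Section 6.1 says "The participant will take 2 capsules with 6-8 oz. of water per headache episode", caps intake at six pills a day, and then says: "If participant takes 6 pills in 1 day this will be defined as 3 headache episodes and the patient will be exited from the study". Appendix B, which section 4.4 tells participants to follow, permits two capsules up to three times a day for headache relief. It does not say that each intake must be for a new headache.

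Section 7.1 plans two secondary analyses that depend on what counts as a headache. One is a longitudinal analysis of participants who report more than one incident. The other is time to intervention, with the clock starting at intake of the test product and only other products counting as the event. Section 7.1 calls the secondary analyses hypothesis generating.

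The forms use onset in two ways. The diary (Appendix E) has separate fields for time of onset and time the product was taken, yet labels the pre-dose rating as pain at onset. The insert (Appendix H) asks when the episode began.

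**The concern.** A dose and a headache are different units, and the definitions merge them. If every intake is an onset, the permission in section 4.3 to dose after each onset cannot separate a second dose for a continuing headache from a first dose for a new one. The pill-count sentence in section 6.1 then calls three intakes in a day three headaches, whether or not they were distinct.

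At stake are the baseline, the clock and the count. A repeat dose filed as a new event has its own pre-dose Mankoski score, which is a post-treatment score for the same headache. Time to intervention may be measured from the latest dose instead of the first. The longitudinal analysis may then describe the course of one headache as a series of headaches.

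**Working it through.** **Do the visible sections separate a dose from a headache?**

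- Sections 4 and 6.1: onset is dosing.
- Section 4.3: use is allowed after each onset, which is circular given that definition.
- Section 6.1: six pills in a day are three episodes. No visible rule covers four.
- Appendix B: up to three intakes a day, with no link to a new headache.
- Section 4.2: "During the 1 hour after taking the test product, no medication or supplementation (including all CBD products) other than the test product should be taken". This limits other products and does not address a further test dose.
- Appendix D offers usual headache durations of over two hours or no resolution, so headaches outlasting the one-hour rating are foreseen.

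No visible section requires the earlier headache to have resolved before a new episode is counted.

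**Could the data separate them afterwards?** Partly. The diary records onset, dosing and resolution times. Section 6.1 says that once the participant's "symptoms resolve, the participant will complete the headache diary", but the schedule in section 6.2 marks the diary only at event start and 60 minutes, so resolution times may be missing.

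**The plan's own figure.** Section 7.2 gives 68 patients for 90% power with mean change 2 and SD 5. Alpha is not stated; assume 0.05 two-sided. For a paired t-test the noncentrality is (2/5) × √68 = 3.30, giving power 0.902, so 68 reproduces. With the 97 treated participants of section 5.1, power is 0.974. Both count one change per participant, so the planned power does not need later episodes.

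**What mislabelling does to one headache (assumed values).** Doses at 0, 2 and 4 hours; pre-dose scores 6, 5 and 4; score 3 one hour after the third dose; another medication at 5.5 hours.

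| | Baseline(s) | Time to other medication |
|---|---|---|
| One headache | 6 | 5.5 h |
| Three episodes | 6, 5, 4 | 5.5 − 4 = 1.5 h for the third; no event before the next dose for the first two |

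**Share of records that are not new headaches, six-pill case.** All inputs are assumed, because the documents give no re-dosing or filing rate. Let p be the share of headaches needing further treatment, r the share of those given two repeat doses, and f the share of repeat doses filed as new entries. Each headache yields 1 + 2prf records, of which 2prf are not new headaches, so the share is 2prf/(1 + 2prf). With f = 1:

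- p = 0.20, r = 0.10: 0.04/1.04 = 0.038, or 4%.
- p = 0.40, r = 0.30: 0.24/1.24 = 0.194, or 19%.
- p = 0.60, r = 0.50: 0.60/1.60 = 0.375, or 38%.

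If r = 0 or f = 0, the share is zero.

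**The case against.** Most of the visible text points to one dose per headache: two capsules per episode in section 6.1, one "Test Product Consumed" mark per event in section 6.2, and in section 6.6 "The three-episode supply of test product will be packaged and labeled with ingredients and a study ID number". For a headache lasting beyond an hour, sections 4 and 4.2 describe other medication as the route. This stands and makes re-dosing less likely, but Appendix B is a participant-facing instruction that reads differently.

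A reader might infer that the plan will analyse repeat doses as separate headaches. The documents do not say so. The pill-count sentence sits in a bullet on dosing and exit, the longitudinal analysis is defined by reported incidents, and section 7.1 does not say that the clock restarts. Both consequences are possible readings that nothing visible rules out.

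A reader might also infer that the counting rule costs the trial second and third treated headaches. It does not: a three-episode supply at two capsules each is 3 × 2 = 6 capsules, so no product remains after six pills in any case.

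Nor is leaving the test product out of the intervention event a fault; section 7.1 defines the event that way on purpose.

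Finally, the insert breaks off after its first instruction step, Appendix 13.1.9 was not available, and section 7.3 defers detailed methods to a later SAP. Any of these may hold a rule.

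**Conclusion.** The conflict in the definitions is plain on the text: onset is dosing in the protocol body but has a second meaning in the forms, and section 6.1 and Appendix B do not agree on whether an intake implies a new headache. The consequence for analysis is conditional. If participants re-dose within a headache and file those doses as new entries, the longitudinal and time-to-intervention results could be distorted. How often this would happen, and in which direction mean change would move, cannot be learned from the documents. The 4% to 38% range rests wholly on assumed rates, and zero is possible.

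A reader might take this as a threat to the primary endpoint. That is not supported unless later episodes enter the paired test. Section 7.2 leaves this open by saying that multiple headaches per patient might add power, and no section says which episode is used. The point is worth correcting because it is cheap to do so, not because the main result is shown to be at risk.

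**What to change.** 1. Reconcile sections 4.3, 6.1 and Appendix B on repeat dosing, and give onset one meaning in the protocol, diary and insert. No dosing or exit rule is proposed here.
2. For analysis, do not define headaches by the pill count. Add one diary item: *Had your previous headache resolved before this dose? Yes / No / This is my first.* Use it with the recorded start, dosing and resolution times. A dose answered No belongs to the earlier headache, with baseline and clock fixed at that headache's first dose. Where resolution status is missing, run the analysis with and without same-day re-doses. A fixed window of 12 to 48 hours is not advised: it could merge genuine separate headaches, since Appendix D allows for daily headaches and for headaches lasting under an hour.
3. State that the primary paired test uses each participant's first headache. The sample size already counts one change per participant, so planned power is unaffected.

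The cost is one diary item, short derivation rules in the SAP, some programming and fewer countable episodes. Repeat doses that are never filed would still be missed, and this should be stated as a limitation.

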6.2 Study Schedule of activities

Assessments	Screening	Consent	Before Receipt of Test Product	Product Received	Event 1	15 Minutes After Event Start	30 Minutes After Event Start	60 Minutes After Event Start
Study Window								
Screening Survey	Х							
Consent		X						
Baseline Survey			Х					
Demographics			Х					
Medications & Supplements			Х					
Acknowledgement of receipt of test product				X				
Headache Diary					X			X
10-point Mankoski Scale					Х	Х	Х	Х
Test Product Consumed					Х			
AE Assessment					X	X	X	X
Study Exit Survey								

Assessments	Event 2	15 Minutes After Event Start	30 Minutes After Event Start	60 Minutes After Event Start	Event 3	15 Minutes After Event Start	30 Minutes After Event Start	60 Minutes After Event Start	Study Exit
Study Window									
Screening Survey									
Consent									
Baseline Survey									
Demographics									
Medications & Supplements									
Acknowledgement of receipt of test product									
Headache Diary	Х			X	Х			X	
10-point Mankoski Scale	X	X	Х	X	X	X	X	X	
Test Product Consumed	Х				X				
AE Assessment	Х	X	Х	X	X	X	Х	X	Х
Study Exit Survey									X

6.3 Participant Enrollment and Follow-Up

Patients suffering from mild to moderate tension headache symptoms will complete a cloud-based, HIPAA-secured screening survey to determine eligibility. All eligibility criteria must be met for participants to be approved for enrollment in the study. Participants will be provided informed consent and the opportunity to ask questions related to the study procedures, risks and benefits, and rights related to participation in the study. Participants who sign the study informed consent will be prospectively enrolled in the study and provided a link to a patient portal, which provides study resources. Participants will take the study formula at the onset of symptoms and provide information related to pain and tension headache symptoms during the follow-up period. A remote study coordinator may prompt participants to provide study information to ensure that the study forms are completed. Efforts will be taken to ensure minimal withdrawals and loss to follow-up.

6.4 Adverse Event and Safety Monitoring

Adverse Events (AEs) are defined as any untoward medical occurrences described by the study participant. All AEs will be self-reported and documented on the platform. The AEs will be reviewed by the study team including the remote trial coordinator and study principal investigator and reported according to the IRB requirements. Participants who experience adverse events will be advised to stop taking the test product and seek medical attention.

In the event that a participant experiences an adverse event, the clinical study manager or clinical ops coordinator will notify both the PI and Sponsor. The Sponsor will take appropriate action according to their standard operating procedures for any adverse events that warrant action by the Sponsor.

6.4.1 Anticipated Adverse Events

Anticipated Adverse Events are complications that are known to be associated with the test product (in high doses exceeding recommended use):

- Diarrhea
- Nausea
- Stomach Cramps
- Acid Reflux
- Skin Rashes
- GI Bleeding
- Headaches
- Liver Damage

6.4.2 Adverse Event Relationship

Each reported AE will be assessed by the Investigator for relatedness, severity and causality.

6.4.3 Serious Adverse Events

A Serious Adverse Event is an Adverse Event that leads to death or to serious deterioration in the health of the participant that either resulted in a life-threatening illness or injury, or a permanent impairment of a body structure or body function.

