- Present intention is that the analysis will be performed in R, and the precise form of algorithms will be the default of R. Kaplan-Meier, log-rank, and proportional hazards algorithms will be the defaults of the survival package. [13]
- The exact items to be compared depend on what is reported in each historical control study. When possible, the items will include symptom relief at each time measured, including within-patient p-values, and time to the lowest level on a 4-point scale and to

the lowest 2 levels on a 10-point scale. as well as reported baseline characteristics. When two-arm studies are compared, both arms will be reported in this comparison. Specific studies to be considered will be identified prior to the analysis of actual trial data.

8 Informed Consent Process

The study protocol and informed consent will be reviewed approved by Advarra Institutional Review Board, prior to study start.

Study candidates will learn about the study via digital advertisements. If interested in learning more, they will be referred to a website "landing page" that will provide detailed information about the study. They may opt to complete a screening survey ascertaining study eligibility through patient reported outcomes. If successfully completed (no exclusion criteria are selected), candidate will be invited to review the study consent form tutorial which includes the opportunity to ask questions related to the study from the Principal Investigator or delegated authority of the investigator. Candidate will be provided with contact information to reach investigator or study manager as desired.

Candidate may sign the informed consent via electronic signature as provided by Hawthorne Effect. The study manager will verify candidate signature prior to enrollment as a study participant.

9 Subject Confidentiality

All participants' data and personal information will be kept confidential. Only those involved with the study will have access to participant information. The data will be stored by Hawthorne Effect on a HIPAA compliant platform. The platform, which the data is stored on, will require a personalized username and password to gain access.

10 Publication

Prior to the first patient enrolled, study will be registered on clinicaltrials.gov and submit the results for advertisement and promotion purposes.

11 Limitations

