
13.1.7Appendix G Adverse Event Form

Tension AE document

- 1. Did you experience any side effects after taking the test product? Y/N
 - a. If so, did you experience any of the following
 - o itching, rash, hives, throat/lip/tongue swelling, wheezing
 - low blood pressure, fainting, chest pain, shortness of breath, palpitations, irregular heart beat
 - o severe, persistent nausea, vomiting, diarrhea, or abdominal pain
 - o difficulty urinating, decreased urination
 - o fatigue, appetite loss, yellowing skin/eyes, itching, dark urine
 - severe joint/muscle pain
 - o slurred speech, one-sided weakness of face, arm, leg, vision
 - o abnormal bleeding from nose or gums
 - o blood in urine, stool, vomit,
 - o marked mood, cognitive, or behavioral changes, thoughts of suicide
 - o Other:
- 2. Please give a description of the event
- 3. How soon after taking the test product did you experience the side effect?
- 4. What did you do to alleviate the side effect?
- 5. Did you have to go to the hospital or see a doctor for this side effect?
 - a. Please describe any diagnosis or treatment that they provided.
 - b. If you were seen in the hospital, please upload any discharge paperwork or other documents from the hospital.

13.1.8Appendix H Test Product Insert

Welcome to the Tension Headache Relief Trial!

We appreciate you taking the time to participate in this trial. As you may already know, the aim of this study is to measure the impact the test product has on your headache symptoms. Please take the time to read the following information below to become acquainted with the trial instructions.

Instructions upon Study Product Receipt:

- 1. Please log onto the study portal and acknowledge the receipt by completing the 'Start Form'
- 2. Enclosed in the study bag, please find a 3-episode supply of the tension relief test product.
- 3. You will take the test product the next time you have a headache and need to take something to relieve the discomfort.

Instructions Once Product Intake Begins:

- 1. The next time you have a headache and feel the need to take the test product, you will FIRST start the headache diary (paper forms included in this package).
 - You will complete the date of the episode, the time the episode began, what triggered the headache, type/description of the pain, its location, and record other symptoms (if applicable).
 - REMINDER: DO NOT TAKE ANY OTHER MEDICATION/SUPPLEMENT DURING THE HOUR AFTER TAKE THE TEST PRODUCT.

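### The serious adverse event definition in Section 6.4.3 omits hospital admission, so an admitted event that is not life-threatening and resolves would be classed as non-serious

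*Combined protocol and SAP*

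**What the plan says.** Section 6.4.3 contains the only definition of a serious adverse event in the supplied text: "A Serious Adverse Event is an Adverse Event that leads to death or to serious deterioration in the health of the participant", where the deterioration must have "either resulted in a life-threatening illness or injury, or a permanent impairment of a body structure or body function". There are thus three routes to seriousness: death, a life-threatening illness or injury, and permanent impairment.

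Appendix G, the participant's adverse event form, asks in item 5: "Did you have to go to the hospital or see a doctor for this side effect". It then asks for any diagnosis or treatment given, and adds: "If you were seen in the hospital, please upload any discharge paperwork or other documents from the hospital".

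Section 6.4.2 describes the medical assessment: "Each reported AE will be assessed by the Investigator for relatedness, severity and causality". Section 6.4 covers routing. When an adverse event occurs, "the clinical study manager or clinical ops coordinator will notify both the PI and Sponsor", and events are to be reviewed by the study team, including the "study principal investigator and reported according to the IRB requirements". The synopsis and Section 3 say that adverse events will be summarised.

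Sections 2.2.1 and 6.4.1 list GI bleeding and liver damage among the possible effects, in both places tied to doses above the recommended use.

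**The concern.** The form collects information on hospital care, and the definition makes no use of it. A participant could be admitted, recover fully without having been in danger of dying, and send in discharge papers. Under Section 6.4.3 that event is non-serious.

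The protocol also assigns the seriousness decision to nobody. The Investigator assesses relatedness, severity and causality. Severity is a separate attribute: a severe event need not meet Section 6.4.3.

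What is at stake is how the safety results read. Section 11 acknowledges that the study rests entirely on self-report, without medical review of symptoms, so hospital documents would be among the few outside records of an event. Section 10 says the sponsor will "submit the results for advertisement and promotion purposes". A statement that no serious events occurred could be true under Section 6.4.3 while the study file held discharge papers from an admission, and a reader of that statement would not know it.

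**Working it through.** The main check is a reading of the text. The plan gives no figure for serious events, so there is none to reproduce.

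**Step 1. Apply Section 6.4.3 to a test case.** A participant is admitted to hospital, is never in a life-threatening state, and recovers without lasting impairment.

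| Route in 6.4.3 | Met? |
|---|---|
| Death | No |
| Life-threatening illness or injury | No |
| Permanent impairment of structure or function | No |

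Result: not serious. If the same event had been life-threatening, the second route would be met and the event would be serious whether or not it later resolved. The gap is therefore confined to admissions that are neither life-threatening nor permanently impairing.

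**Step 2. Look for another rule that would catch the case.**
- Section 6.4.2 names three assessments, and seriousness is not one of them.
- Section 6.4 refers to IRB requirements, and Section 2.2.3 to 21CFR and GCP. Neither section states another definition of seriousness.
- Appendix G item 5 records the hospital contact, but no section says what follows from the answer.

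Result: within the documents, Section 6.4.3 decides the case alone.

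**Step 3. Ask whether the form could support an admission criterion as it stands.** Item 5 puts going to hospital and seeing a doctor into one question. Its follow-up refers to being seen in hospital, which could be an emergency or outpatient visit. Result: admission cannot be identified reliably from the form.

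**Step 4. Illustrate the effect of one reclassified event.** Inputs: n = 97, the desired number of treated participants (Section 5.1); exact two-sided 95% limits, in line with the exact intervals that Section 7.3 plans for discrete variables; one hypothetical admitted event, which is my assumption.

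- Zero events: upper limit = 1 − 0.025^(1/97) = 0.0373, or 3.7%.
- One event: point estimate 1/97 = 1.0%. The upper limit u solves (1 − u)^97 + 97·u·(1 − u)^96 = 0.025. At u = 0.056 the left side is 0.0037 + 0.0215 = 0.0252, just above 0.025, and the solution is u = 0.0561, or 5.6%.

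One classification decision moves the estimate from 0% to 1.0% and the upper limit from 3.7% to 5.6%.

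**The case against.** The strongest reply is that nothing in the plan depends on the label. Section 6.4 sends every adverse event to the principal investigator and the sponsor, serious or not, and has it reported as the IRB requires. Section 6.4.2 has each one graded for severity. The synopsis and Section 3 promise a summary of adverse events and plan no separate serious event rate. All of this stands: the event would not be lost, and its handling would not change.

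Four stronger readings are tempting, and the documents do not support them.

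- A reader might infer that Section 6.4.3 and Appendix G contradict each other. They do not. A form may collect a fact that a definition does not use, and no section says that hospital care makes an event serious. The definition is narrow and the form is not linked to it.
- A reader might infer that any hospitalised event that resolves would be non-serious. The life-threatening route catches some of these regardless of outcome.
- A reader might infer that the safety summary underpins the minimal-risk determination. Section 2.2.1 records that determination in advance, by the sponsor and principal investigator, and it does not rest on this trial's adverse event results.
- A reader might take GI bleeding and liver damage as expected at the study dose. Sections 2.2.1 and 6.4.1 list them for high doses exceeding recommended use, so they show the kind of event at issue and give no expected frequency.

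It could also be said that the cited IRB, 21CFR or GCP rules use a wider definition. They may, but the documents do not reproduce one. If a wider definition is meant to apply, Section 6.4.3 should state it.

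**Conclusion.** The point holds in a limited form. As written, Section 6.4.3 would class as non-serious an event that leads to hospital admission, is not life-threatening and resolves without permanent impairment. Nothing else in the documents changes that result, and no section assigns the seriousness decision.

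The effect is confined to the event's classification and any serious event count that is reported. Notification, review, the adverse event summary and the primary efficacy analysis are untouched. The figures of 3.7% (0/97) and 5.6% (1/97) rest on two assumptions: that 97 participants are treated, which is a desired number and not a fixed denominator, and that one such event occurs. The documents give no expected rate, so these limits show how far one decision moves the result and do not predict that it will arise.

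**What to change.** Reconcile Sections 6.4.2 and 6.4.3 with Appendix G, for classification and reporting only:

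1. Add a sentence to Section 6.4.3 making an adverse event that leads to hospital admission a serious adverse event.
2. Split Appendix G item 5 into two answers: admitted to hospital; and seen by a doctor, or in hospital, without admission.
3. Add seriousness to the Investigator's assessment in Section 6.4.2, and say that the item 5 answer and any uploaded hospital papers inform it.

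The cost is one sentence, one split question and one added word in the assessment list. The downside for the sponsor is that the reported serious event count may rise. No dose, treatment or stopping rule is affected.
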